Chronic kidney disease (CKD) is common in Hepatitis C virus (HCV) infected individuals. Between 55-85% of HCV infected patients with cirrhosis have some form of glomerular disease on kidney biopsy.^[1, 2] It is well established that HCV increases the risk of progressive CKD; patients with HCV are 34-68% more likely to develop end-stage-renal disease (ESRD) than non-infected patients.^[3-5] Despite the advances in all oral therapies for HCV infection over the last 2 years, there is still tremendous need for data to guide how to treat HCV infected patients with advanced kidney disease. The Abbvie Viekira Pak was approved by the FDA on December 19th, 2014 to treat genotype 1 infection and Mavyret, a pangenotypic combination regimen of glecaprevir and pibrentasvir, was approved in August 2017 with no dose adjustments necessary for mild to severe renal impairment. However no published series have looked explicitly at this population to determine the effect on historical and novel biomarkers of CKD and renal inflammation. Historically, achieving sustained virologic response (SVR), with pegylated interferon and ribavirin therapy has been shown to improve kidney function and decrease the rate of progression of CKD.^[6-10] The mechanism behind the link between HCV infection and CKD progression is not fully understood, but likely involves promotion of insulin resistance, chronic inflammation, and the potential for immune complex deposition in the glomerulus of the kidney. The new era of DAA therapy allows for the opportunity to better characterize the mechanisms that promote CKD by studying the reversibility of markers of kidney disease and chronic inflammation with eradication of HCV. We hypothesize that patients with advanced CKD will demonstrate improvement in proteinuria and eGFR after viral eradication with either Viekira Pak or Mavyret per current standard of care guidelines found at HCVguidelines.org.

The new era of HCV therapy allows us to test the reversibility of the association between HCV infection and CKD. Our data in patients with cryoglobulinemia shows that patients with active glomerulonephritis treated with novel direct antiviral agents (DAA) had a 70% reduction in proteinuria and a 12.6mL/min improvement in eGFR by SVR12^[11]. Reduction in proteinuria is an important component of the definition of clinical remission in treatment of glomerular diseases and a widely accepted surrogate for CKD progression.^[12, 13]

Cystatin-C based eGFR estimates have been shown to outperform creatinine-based estimates in terms of predicting cardiovascular events and mortality; this is likely related to the fact that in addition to measuring kidney function, serum cystatin-C also reflects the inflammatory milieu.^[14-18] Urine studies, such as albuminuria and proteinuria are heavily relied on by nephrologists to predict which patients are going to develop progressive CKD. Albuminuria is common in HCV infection, however it is typically not screened for, nor routinely monitored in patients with HCV infection undergoing therapy.^[19, 20] Citations for the rationale for measuring novel CKD biomarkers are listed below.

It is well established that HCV infection is a risk factor for CKD progression. We propose that this data could serve as the basis to support further study into the role of HCV eradication to slow CKD progression in patients with HCV. If HCV is a reversible risk factor for progressive CKD, then the implications of this finding will be far-reaching. Slowing progression of kidney disease is a critical goal in the field of nephrology, as the increasing incidence and prevalence of advanced CKD and ESRD places significantly increased health burden on patients and tremendous costs on our health-care system.

Section 3. Core Protocol

3.1 Study Objectives and Purpose:

The objective of this study is to evaluate the effect of HCV eradication with Viekira Pak or Mavyret for adults with CKD with an estimated glomerular filtration rate (eGFR) 15-60 ml/min that are infected with hepatitis C virus (HCV) genotype 1-6, to determine the effect of treatment on traditional and novel markers of kidney function and cardiovascular disease risk in patients with advanced CKD. During the course of this prospective, single arm treatment trial, we will measure currently accepted markers of kidney function and novel biomarkers of CKD progression to determine if they improve with eradication of HCV.

Aim 1. Determine the effect of HCV eradication with Viekira Pak or Mavyret on traditional and novel markers of CKD progression in 10 patients with CKD (eGFR 15 - 60) who are pre-dialysis who undergo therapy of HCV infection. Measure novel biomarkers of incident and progressive CKD and liver disease to determine if eradication of HCV infection changes measures of chronic inflammation associated with progressive end-organ disease. Repeated measures will be taken at baseline and regular study intervals.

Aim 1. Determine the safety, tolerability, efficacy, and effect on quality of life of Viekira Pak or Mavyret in 10 patients with CKD (eGFR 15 – 60mL/min) who are pre-dialysis. Patient visits at baseline, week 2, 4, 8, 12, and SVR 12 to assess safety, adverse reactions, and perform measurements for Aim 1.

We hypothesize that that traditional and novel markers of CKD will improve with HCV eradication and that Viekira Pak or Mavyret will be safe and effective and lead to improvement in quality of life in patients with advanced CKD.

3.2. Study Design

This will be a single arm, open-label experimental trial conducted at Massachusetts General Hospital. There will be no control or placebo arm. Massachusetts General Hospital will be the single study center

Ten patients with CKD (estimated glomerular filtration rate (eGFR) between 15mL/min and 60mL/min. We expect 5 patients with have stage 3b or 4 CKD (GFR 15-45) and 5 patients will have stage 3A CKD (eGFR 45-60). Due to the fact that the vast majority of patients with eGFR < 20mL/min are referred for kidney transplant evaluation and strongly encouraged to undergo transplantation from HCV infected donors prior to receiving DAA therapy in order to dramatically shorten transplant waitlist time, this pool of patients is largely left untreated at the request of our transplant center. This significantly limits our ability to recruit patients whose GFR is approaching 20mL/min. Thus, in order to complete this study in a timely fashion, we propose including patient with eGFR up to 60mL/min to improve our ability to rapidly recruit patients into this study. Futhermore, stage 3A and 3B CKD are the stages where interventions such as eradicating HCV are most likely to be able to slow eGFR decline this is an important population to study.

If eligible, they will undergo treatment. The expected duration of study participation is 58 weeks, this time period includes a 30 day screening period, followed by 12 weeks of therapy with Viekira Pak or Mavyret and a total of one year of follow-up. A study timeline is provided showing the sequence and duration of all study periods.

Figure 1. Study Timeline

365
[1yr f/u]

3.3 Inclusion Criteria

1. The subject has signed the written informed consent
2. Male or female ≥ 18 year of age
3. HCV genotype 1-6 with ribonucleic acid (HCV RNA) greater than 1000IU/mL, determined by HCV RNA polymerase chain reaction Roche COBAS TaqMan quantitative assay
4. Women of childbearing potential (i.e. women who have not undergone hysterectomy or bilateral oophorectomy, or no medically documented ovarian failure, and are ≤ 50 years of age) must agree to 1 medically approved contraceptive measures and have their partners agree to an additional barrier method of contraception for the duration that they take Viekira Pak or Mavyret and 90 days after finishing Mavyret. If their regimen includes ribavirin, they must agree to this for 6 months after the last administration of the study drug. Women of childbearing potential must not rely on hormone-containing contraceptive as a form of birth control during the study but may use. An intrauterine device, female barrier methods with cervical cap or diaphragm with spermicidal agent, tubal sterilization, or vasectomy in male partners

5. Male subjects must agree to consistently and correctly use a condom during heterosexual intercourse and avoid sperm donation for the duration that they take Viekira Pak or Mavyret and 90 days after finishing Mavyret. If their regimen includes ribavirin, they must agree to this for 7 months after the last dose of if ribavirin. Additionally, if their female partner is of childbearing potential (as defined above), their partner must agree to use either 1 of the non-hormonal methods of birth control listed above or a hormone-containing contraceptive for 7 months after last study drug date. Hormone-containing contraceptive options for partners include implants of levonorgestrel, injectable progesterone, oral contraceptives, contraceptive vaginal ring, or transdermal contraceptive patch
6. Estimated glomerular filtration rate 15-60mL/min/1.73m² as estimated by CKD-Epi equation ^[22]
7. Liver imaging to exclude HCC is required within 6 months in any patient with cirrhosis

[figure not shown]
3.4 Exclusion Criteria

Subjects who meet any of the following exclusion criteria will not to be enrolled in this study

1. History of evidence of clinically significant disorder other than hepatitis C virus infection or clinically significant laboratory finding that in the investigator's judgment would pose a risk to subject safety, interfere with study procedures, or prevent completion of the study
2. History of decompensated cirrhosis, Child-Pugh Class B/C cirrhosis
3. Pregnant or lactating female
4. Uncontrolled depression or psychiatric disease interfering with the ability to comply with the study procedures or complete the study
5. History or presence of any form of cancer within 3 years prior to enrollment, with the exception of excised basal cell or squamous cell carcinoma of the skin, stage 0 or 1 melanoma, or cervical carcinoma in site or breast carcinoma in situ that has been excised or resected completely and is without evidence of local recurrence or metastasis
6. Experiencing life-threatening cryoglobulinemic vasculitis requiring initiation of rituximab, steroids or plasmapheresis.
7. Concomitant use of red yeast rice, St. John's Wort, Carbamazepine, phenytoin, pentobarbital, phenobarbital, primidone, rifabutin, rifampin, efavirenz, atorvastatin, lovastatin, simvastatin during the study period. Use of pravastatin allowed if dose reduced by 50% and rosuvastatin allowed up to a dose of 10mg daily if taking Mavyret. Concomitant use of alfuzosin, carbamazepine, ergot derivatives, ethinyl estradiol containing products, efavirenz, gemfibrozil, lovastatin, midazolam, phenobarbital, phenytoin, pimozone, rifampin, sildenafil, simvastatin, St. John's wort, triazolam if taking Viekira Pak.
8. Uncontrolled cardiovascular or pulmonary disease
9. Known hypersensitivity to ribavirin, dasabuvir, ombitasvir, paritaprevir or ritonavir
10. Experiencing symptoms attributed to uremia: nausea, vomiting, asterixis, and pericardial effusion without another cause.
11. Treating nephrologist anticipates the need to begin renal replacement therapy in the next 6 months
12. Inadequate hematologic parameters defined as follows platelets < 50 x 10⁹/L or hemoglobin < 9 g/dL despite use of erythropoietin stimulating agent
13. Previously treatment experienced with a NS5A inhibitor class medication or previously treated with Mavyret
14. Patients with genotype 3 infection with any direct-acting antiviral exposure will be excluded.
15. Kidney transplant recipient

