3.6 Study Procedures

This will be a single-arm unblinded trial evaluating the safety and efficacy and effects of HCV eradication with Viekira Pak or Mavyret on kidney function and markers of CKD progression.

Initial Screening Period

Patients will be asked to perform two screening visits. At the first visit they will be screened for eligibility according to the above inclusion and exclusion criteria. They will also have screening blood and urine tests performed. Patients will undergo Fibroscan to determine the degree of cirrhosis unless they have a prior biopsy documenting cirrhosis. At this visit they will undergo informed consent and participant and investigators will each receive a copy of the signed consent form. The primary purpose of the second screening visit is to establish a stable baseline level of renal function including cystatin C and creatinine based estimated GFR estimate and proteinuria level.

Baseline Visit

At the baseline visit, patients will undergo full medical history and physical examination, ECG monitoring, quality of life assessment with SF36 and FACIT-F (a fatigue scale). Patients will undergo venous sampling for routine bloodwork and sampling of blood and urine for study assays (**Table 1a and 1b**). Patients will receive the first four weeks of study drug at the baseline visit.

Table 1a. Traditional Markers of CKD Progression

Measured at Baseline, Week 4, Week 8, Week 12 or 16 (if needed), SVR4, SVR12, SVR24 and 1 year

Serum creatinine (mg/dL)
Serum cystatin C (mg/L)
Urine total protein (mg/dl) / urine creatinine (mg/dl) ratio
Urine albumin (mg/dl) / urine creatinine (mg/dl) ratio
White blood cell differential – monocyte count linked to CKD progression and atherosclerosis ^[23]

Table 1b. Novel Markers of CKD Progression
Measured at Baseline, Week 8, SVR12, and 1 year follow-up

Serum FGF-23– validated marker of incident and progressive CKD ^[24]
Serum CRP – marker of incident and progressive renal failure ^[25, 26]
Serum and Urine IL-6 - marker of incident and progressive renal failure ^[25, 26]
TNF-alpha receptor - marker of incident renal failure ^[26]
Soluble CD163 – liver fibrosis, marker of macrophage activity, implicated in mechanism of immune complex kidney disease ^[27]
Urine neutrophil gelatinase associated lipocalin (NGAL) – correlates with more advanced fibrosis on kidney biopsy ^[28] and with incident CKD ^[29] and cardiovascular mortality in CKD ^[30] .

Dosing regimen

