Patients will be prescribed DAA therapy (Viekira Pak or Mavyret) based on current standard of care. We will submit the prescription for approval by their insurance company. If insurance approval is denied, or if the patient is uninsured, the treatment course will be provided by Abbvie.

On label use of the Viekira or Mavyret regimen will follow recommendations provided by the AASLD and IDSA, (HCVguidelines.org, accessed 10/11/17).

Patient receiving Mavyret:

1. Genotype 1-6 noncirrhotic, treatment naïve patients will receive 8 weeks of Mavyret
2. Genotype 1-6 with cirrhosis, treatment naïve patients will receive 12 weeks of Mavyret
3. Genotype 1, 2, 4, 5, 6 patients treatment experienced with either interferon, ribavirin, sofosbuvir, or a protease inhibitor will receive 12 weeks of Mavyret
4. Genotype 3 patients that are treatment experienced with either interferon and/or ribavirin will receive 16 weeks of Mavyret

Patients receiving Viekira-Pak based regimens:

Genotype 1a - Paritaprevir (150mg)/ritonavir (100mg)/ombitasvir (25mg), once daily, dasabuvir (250mg) twice daily, ribavirin 200mg-400mg daily (based on eGFR) for 12 weeks. Excluded if cirrhotic.

Genotype 1b. Paritaprevir (150mg)/ritonavir (100mg)/ombitasvir (25mg) once daily, dasabuvir (250mg) twice daily for 12 weeks. Ribavirin 200mg daily added if there is a history of cirrhosis. Initial Ribavirin dosing will follow package insert and begin with 200mg daily for patients with $<30\text{mL}/\text{min}/1.73\text{m}^2$. Dose adjustments for anemia will follow published guidelines.[30]

Genotype 4 – Paritaprevir (150mg)/ritonavir(100mg)/ombitasvir (25mg) once daily and ribavirin 200-400mg (based on eGFR) once daily for 12 weeks.

On-Treatment Follow-up visits – Treatment period will be based on standard of care for all subjects
Patients will undergo a follow-up visit at 2 weeks, 4 weeks, 8 weeks and 12 and 16 weeks if needed on therapy and monitoring for adverse events by the study investigators with history and targeted physical exam and with routine bloodwork will occur at every study visit. Routine 12 lead ECG will be monitored on week 2 and end of treatment. Quality of life measures will be taken at 8 weeks on therapy. Traditional CKD biomarkers (**Table 1a**) will be measured at week 4, 8, and 12. Novel biomarkers (**Table 1b**) will be measured at week 8 on treatment.

Post-Treatment Follow-up Visits

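### Exclusion criterion 9 was not aligned with Mavyret: for Mavyret-only patients it screens for five drugs they will not receive and neither of the two they will

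*Combined protocol and SAP*

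**What the plan says.** Criterion 9 in section 3.4 (Exclusion Criteria) reads "Known hypersensitivity to ribavirin, dasabuvir, ombitasvir, paritaprevir or ritonavir". The lead-in to that section bars a subject who meets any one criterion, and criterion 9 is not limited to a particular regimen.

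The trial uses two treatments. The background describes Mavyret as "a pangenotypic combination regimen of glecaprevir and pibrentasvir". Section 3.6 (Study Procedures, Dosing regimen) gives four Mavyret rules, which together cover genotypes 1 to 6, and none adds ribavirin. Two of them concern previously treated patients. For genotypes 1, 2, 4, 5 and 6, "patients treatment experienced with either interferon, ribavirin, sofosbuvir, or a protease inhibitor will receive 12 weeks of Mavyret". For genotype 3, "Genotype 3 patients that are treatment experienced with either interferon and/or ribavirin will receive 16 weeks of Mavyret".

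The Viekira-based regimens in the same section are given for genotypes 1a, 1b and 4 only. The genotype 1a entry ends "ribavirin 200mg-400mg daily (based on eGFR) for 12 weeks. Excluded if cirrhotic".

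Other eligibility items do take account of the regimen or of Mavyret:

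- On contraception, inclusion criterion 4 says "If their regimen includes ribavirin, they must agree to this for 6 months after the last administration of the study drug", and inclusion criterion 5 has a similar ribavirin condition.
- Exclusion criterion 7 has separate lists of prohibited drugs for Mavyret and for Viekira Pak.
- Exclusion criterion 13 bars patients "Previously treatment experienced with a NS5A inhibitor class medication or previously treated with Mavyret".

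**The concern.** A hypersensitivity exclusion should protect patients from the drugs the trial will give them. For a patient who can receive only Mavyret under this protocol, criterion 9 does not do that. It turns the patient away for intolerance of drugs outside the assigned regimen and does not name the drugs inside it.

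What is at stake is chiefly recruitment. The trial plans ten patients, and section 3.2 says recruitment is constrained and gives that as the reason for admitting patients with eGFR up to 60 mL/min. An exclusion with no treatment reason works against that aim. The omission of glecaprevir and pibrentasvir is a secondary safety point.

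**Working it through.** No sample-size, power or error-rate figure is involved. The check sets the drugs named in criterion 9 against the components of each regimen in section 3.6.

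**Inputs**

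- Drugs named in criterion 9 (section 3.4): ribavirin, dasabuvir, ombitasvir, paritaprevir, ritonavir. Count: 5.
- Components of Mavyret (background): glecaprevir, pibrentasvir. Count: 2.
- Eligible genotypes (section 3.3, criterion 3): 1 to 6. Count: 6.

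**Step 1: which patients have only Mavyret listed.** Viekira-based regimens exist for 1a if not cirrhotic, for 1b and for 4. Removing these from the eligible set leaves genotypes 2, 3, 5 and 6, which is 4 of 6, plus cirrhotic 1a.

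**Step 2: overlap between criterion 9 and the treatment given.**

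| Regimen and group | Criterion 9 drugs that are given | Drugs given that criterion 9 names |
|---|---|---|
| Mavyret (the only option for genotypes 2, 3, 5, 6 and cirrhotic 1a) | 0 of 5 | 0 of 2 |
| Viekira-based, non-cirrhotic 1a | 5 of 5 | 5 of 5 |
| Viekira-based, cirrhotic 1b | 5 of 5 | 5 of 5 |
| Viekira-based, non-cirrhotic 1b (no ribavirin) | 4 of 5 | 4 of 4 |
| Viekira-based, genotype 4 (no dasabuvir) | 4 of 5 | 4 of 4 |

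The criterion fits the Viekira-based regimens well and does not fit Mavyret at all.

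**Step 3: a concrete case.** Take a genotype 3 patient previously treated with interferon and ribavirin, in whom ribavirin hypersensitivity became known.

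- The genotype 3 dosing rule assigns 16 weeks of Mavyret without ribavirin.
- Criterion 13 does not apply: there has been no NS5A inhibitor and no Mavyret.
- Criterion 14, which removes genotype 3 patients with direct-acting antiviral exposure, does not apply.
- Criterion 9 does apply and bars the patient, for a drug that would not be given.

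Patients with this kind of history are foreseen: 2 of the 4 Mavyret dosing rules are written for groups that include ribavirin-experienced patients.

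**Step 4: can the group be identified in time?** Genotype is part of inclusion criterion 3. Cirrhosis status is settled at screening: "Patients will undergo Fibroscan to determine the degree of cirrhosis unless they have a prior biopsy documenting cirrhosis". Study drug is first handed out at the baseline visit. A Mavyret-only patient can therefore be recognised before treatment starts.

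**Step 5: scope.** For genotypes 1b, 4 and non-cirrhotic 1a, either treatment is listed and the documents do not say when the choice between them is fixed. A criterion covering the Viekira components is defensible there while the choice is open, so needless exclusion is not claimed for those patients.

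**The case against.** The strongest reply is that the mismatch is real on paper but hardly matters.

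- **The safety gap is nearly empty.** Criterion 13 excludes everyone previously treated with Mavyret, so known hypersensitivity to its components is improbable among those who remain. Criterion 1 (investigator judgment) and on-label prescribing add further protection. This stands. None of these, however, can readmit a patient whom criterion 9 has excluded.
- **The over-exclusion is mainly about ribavirin.** A genotype 3 patient who learned of a Viekira hypersensitivity by taking Viekira Pak is already barred by criterion 14. This also stands and narrows the practical effect, but it does not touch the ribavirin case.
- **No affected patient is shown.** The figure of 4 of 6 counts genotypes, not patients, and the trial has only ten patients. This is correct, and it is why the point is rated minor.
- **Dosing rules do not set eligibility.** Treating ribavirin-experienced patients while excluding those hypersensitive to ribavirin is not a logical contradiction. That is fair. The objection to criterion 9 is that the exclusion serves no purpose when the regimen contains no ribavirin.
- **Subtype timing is not stated.** Inclusion criterion 3 asks for genotype without mentioning 1a or 1b. The gap is minor, because section 3.6 itself uses 1a and 1b to decide treatment, so subtype must be known before prescribing.
- **One uniform exclusion is simpler, and the regimen may not be settled at the first screening visit while insurance approval is pending.** Simplicity is a legitimate preference. But other criteria already depend on the regimen, and criterion 9 can be confirmed at any time before drug is dispensed at baseline.

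**Conclusion.** The concern holds as a minor drafting error with a real, if small, effect on who may be enrolled. As written, criterion 9 names 0 of the 2 drugs that Mavyret-only patients will receive, and all 5 of the drugs it does name are ones they will not receive. The group comprises genotypes 2, 3, 5 and 6 and cirrhotic 1a.

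The conclusion rests on two readings of section 3.6. First, the cirrhosis note under genotype 1a rules out the Viekira regimen, not trial entry; this is the natural reading, since a Mavyret rule covers cirrhotic patients of all genotypes. Second, the listed regimens are the complete set.

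How many patients would be affected cannot be derived, because the documents give neither a genotype mix nor a hypersensitivity rate. Sample size and analysis are not affected.

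**What to change.** Replace criterion 9 with wording tied to the treatment, for example:

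> Known hypersensitivity to any component of the regimen to be prescribed (Viekira Pak-based: paritaprevir, ritonavir, ombitasvir, and dasabuvir and ribavirin if included; Mavyret: glecaprevir, pibrentasvir).

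This removes the needless exclusion, names the two missing drugs and still protects every patient who will receive Viekira Pak or ribavirin. Where either regimen is possible, the criterion should be confirmed once the regimen is chosen and before drug is dispensed at baseline.

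The cost is one line in section 3.4. No new test or visit is needed, and sample size and analysis stay as they are. Adding only the two Mavyret components to the existing list would close the safety gap but leave the needless exclusion in place.
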